### List of abbreviations

AE ALS ALAT ALSFRS-R AMG ASAT CK CRF CV DMP DSMB EC/IEC eCRF fALS FAS FPI GCP GCP-V Hb HCG Hct ICH	Adverse event Amyotrophic lateral sclerosis Alanine-Aminotransferase ALS Functional Rating Scale – Revised German drug law (Arzneimittelgesetz) Aspartate-Aminotransferase Creatinkinase Case report form Curriculum vitae Data Management Plan Data Safety and Monitoring Board Ethics committee/Independent ethics committee Electronic case report form Familial amyotrophic lateral sclerosis Full Analysis Set First patient in Good clinical practice GCP regulation Hemoglobin Human Choriongonatropin Hematocrit International conference on harmonization of technical requirements for registration of
IMP	pharmaceuticals for human use Investigational medicinal product
INN	International nonproprietary name
IRB	Institutional review board
ISF	Investigator site file
ITT	Intention-To-Treat
IZKS	Interdisciplinary Center for Clinical Trials
LKP	Clinical Trial Director according to AMG (Leiter der Klinischen Prüfung)
LPI	Last patient in
LPO	Last patient out
MAO	Monoaminooxidase
MCH	Mean corpuscular/cellular hemoglobin
MCHC	Mean corpuscular/cellular hemoglobin concentration
MCV	Mean cell volume
MedDRA	Medical dictionary for regulatory activities terminology
PLT	Thrombocytes, platelets
PPS	Per-protocol analysis set
RBC	Red blood cells
SAE SAP	Serious adverse event
SAP	Statistical analysis plan Source data verification
SEIQoL	Schedule for the Evaluation of Individual Quality of Life
SmPC	Summary of product characteristics
SOP	Standard operating procedure
SUSAR	Suspected unexpected serious adverse reaction
sVC	Slow vital capacity
TMF	Trial master file
WBC	White blood cells

# Synopsis

Title	Efficacy, Safety and Tolerability Study of 1 mg Rasagiline in Patients with Amyotrophic Lateral Sclerosis (ALS) Receiving Standard Therapy (Riluzole)
-	- An AMG Trial with a market authorized substance
Short title	RAS-ALS Trial
EudraCT	2011-004482-32
Sponsor trial code	RAS-ALS
IZKS trial code	2011-013
Indication	Amyotrophic Lateral Sclerosis (ALS)
Phase	IIb
Treatments	Test product: Rasagiline 1 mg over 18 months Control: Placebo Standard therapy: Riluzole 100 mg
Primary objective	Efficacy of rasagiline as add-on therapy to standard therapy with riluzole in patients with ALS compared to placebo in terms of survival (mortality exclusively defined as death).
Secondary objectives	
 
Secondary objectives are to assess:
 
the change of total score of ALS Functional Rating Scale – Revised (ALSFRS-R)
 
the change in individual Quality of Life (SEIQoL, Schedule for the Evaluation of Individual Quality of Life)
 
the change of the slow vital capacity (sVC)
 

Trial design	Multicenter, randomized, stratified, parallel-group, double-blind, placebo-controlled phase IIb-study
Trial population	
 
Main inclusion criteria:
 
Patients meeting all of the following criteria will be considered for enrollment to the trial:
 
possible, probable (clinically or laboratory) or definite ALS according to the revised version of the El Escorial World Federation of Neurology criteria
 
disease duration more than 6 months and less than 3 years (inclusive). Disease onset defined as date of first muscle weakness, excluding fasciculations and cramps
 
vital capacity more than 50% of normal (slow vital capacity; best of three measurements)
 
age: ≥ 18 years
 
continuously treated with 100 mg riluzole for at least four weeks
 
capable of thoroughly understanding all information given and giving full informed consent according to GCP
 
women of childbearing age must be non-lactating and surgically sterile or using a highly effective method of birth control and have a negative pregnancy test
 
 Main exclusion criteria: Patients presenting 1 of the following criteria will not be enrolled in the trial: 
 
previous participation in another clinical study within the preceding 12 weeks
 
tracheostomy or assisted ventilation of any type during the preceding three months
 
gastrostomy
 
any medical condition known to have an association with motor neuron dysfunction which might confound or obscure the diagnosis of ALS 
 
presence of any concomitant life-threatening disease or impairment likely to interfere with functional assessment
 
patients on sandpendirine
 
patients on serotonin neuptake inhibitors (SSRIs), including fluoxetine or fluvoxamine
 
patients on serotonin noradrenalin reuptake-inhibitors (SNRIs) and patients on tricyclic and tetracyclic antidepressants
 

	
 
inhibitors (selective or non-selective)
 
confirmed hepatic insufficiency or abnormal liver function (ASAT and/or ALAT greater than 3 times the upper limit of the normal range)
 
renal insufficiency (serum creatinine more than 2.26 mg/dL)
 
evidence of major psychiatric disorder or clinically evident dementia precluding evaluation of symptoms
 
known hypersensitivity to any component of the study drug
 
liable to be not cooperative or comply with the trial requirements (as assessed by the investigator), or unable to be reached in the case of emergency
 
female with childbearing potential, if no adequate contraceptive measures are used
 
pregnancy or breast-feeding females
 

Trial duration and dates	duration of treatment will be 18 months, the period for cleaning the data, carrying out statistical analyzes, and writing the final study report will be 12 months.
Number of patients	It is planned to enroll 250 patients (2 x 125 patients)
Number of sites	About 15 trial sites in Germany are planned to participate.
Primary endpoint	Primary efficacy endpoint: survival time (time to death).
Secondary endpoints	
 
Key secondary endpoints(s):
 
change of total score of ALS Functional Rating Scale - Revised (ALSFRS-R)
 
change in individual Quality of Life (SEIQoL, Schedule for the Evaluation of Individual Quality of Life)
 
change of the slow vital capacity (sVC)
 

Safety variables	Vital signs Safety laboratory parameters Terms, frequency, relationship and seriousness of adverse events (AEs), and serious adverse events (SAEs)
Statistical analysis	
 
Efficacy: The ITT analysis of the primary endpoint will be done in a confirmatory manner. All other analyzes of primary endpoint, all analyzes of the secondary endpoints, and all safety analyzes are exploratory. For confirmatory data analysis, the log-rank test (one-sided) will be performed. Additionally, the difference in the survival rate (18 months survival) between control group and experimental group will be calculated, incl. 97.5% confidence interval.
 
For further analyzes of primary endpoint, Kaplan-Meier-plots and log-rank-tests will be used.
 
Secondary endpoints: The secondary endpoints will be analyzed descriptively. Differences between experimental group and control group will be investigated using the Mann-Whitney-U-test.
 
Safety: Listing of adverse events, performing of chi-square tests to compare frequencies between control group and experimental group.
 

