#### 6.2.2.3 Period of observation

In this trial, the period of observation for collection of adverse events extends from the time the patient has signed the informed consent document up to 14 days after the patient has routinely or prematurely terminated the study.

If the investigator detects a serious adverse event in a trial patient after the end of the period of observation, and considers the event possibly related to the prior trial, he should contact the sponsor to determine how the adverse event should be documented and reported.

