## 7.1 Sample size

The sample size calculation is based on a comparison of two survival curves using the one-sided log-rank test. Following assumptions were made: Type one error 0.025, power 0.80, recruiting time 6 months, length of follow up period 18 months, 18 month survival rate of 70 % in the control group, 18 month survival rate of 85 % in the experimental group. Under the assumption of equal number of patients in each group, this scenario requires 106 patients in each group, i.e.  $2 \times 106 = 212$  patients in whole trial.

A previous study [GERP ALS-Study; pioglitazone in ALS; NCT00690118, clinicaltrials.gov ID] showed a drop-out rate of about 15 %, screening failure was observed in about 10 %. Thus, in total 250 patients have to be allocated (with consideration of a drop-out rate) and a total number of 278 patients have to be assessed for eligibility.

The sample size calculation was performed using SAS® software, version 9.2, procedure power.

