## 7.4 Analysis of adverse events

All summaries and listings of safety data will be performed for the safety population.

Frequencies of patients experiencing at least one adverse event (AE) will be displayed by body system and preferred term according to MedDRA terminology. Detailed information collected for each AE will include: A description of the event, duration, whether the AE was serious, intensity, relationship to trial drug, action taken, clinical outcome. Summary tables will present the number of patients observed with AEs and corresponding percentages. Additional subcategories will be based on event intensity and relationship to trial drug.

A patient listing of all AEs will be prepared.

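### Adverse events are compared by chi-square on crude patient counts although time at risk depends on survival, the primary endpoint; adding a time-at-risk comparison would be a cheap, minor improvement.

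*Protocol*

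**What the plan says.** The statistical analysis entry of the protocol's synopsis plans, for safety, a listing of adverse events and "performing of chi-square tests to compare frequencies between control group and experimental group". The same entry states that "all safety analyzes are exploratory".

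Section 7.4 describes the same analysis without naming a test: "Frequencies of patients experiencing at least one adverse event (AE) will be displayed by body system and preferred term", and "Summary tables will present the number of patients observed with AEs and corresponding percentages". The unit is therefore the patient with at least one event and the denominator is the number of patients. Neither place mentions time at risk.

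Section 6.2.2.3 collects AEs from consent "up to 14 days after the patient has routinely or prematurely terminated the study". For a patient who dies or drops out, collection stops early.

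Section 7.1 plans on "18 month survival rate of 70 % in the control group" and "18 month survival rate of 85 % in the experimental group".

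**The concern.** Section 2.3 bases the assessment of tolerability and safety on comparing, among other things, AE incidence between the two groups. A crude proportion mixes two things: how often events occur while a patient is under observation, and how long the patient is under observation. In this trial the second is driven by death, which the drug is meant to delay. If the drug works as planned, rasagiline patients are observed for longer. An event that occurs at the same rate in both arms then shows up in a larger share of rasagiline patients. The chi-square test can flag that excess although the drug did not raise the event rate. At stake is how an exploratory safety table is read, not the primary conclusion.

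The test is named in the synopsis, so this is a stated method and not a detail left open. Section 7.4 does not repeat it, so the two places need aligning in any case.

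**Working it through.** **Inputs from the protocol.** 18-month survival 70% (control) and 85% (rasagiline); "Type one error 0.025, power 0.80, recruiting time 6 months, length of follow up period 18 months"; one-sided log-rank test; drop-out 15%; screening failure 10% (all 7.1). 125 patients per group (3.2). 18 months of treatment per patient (3.1).

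**Assumed.** Exponential survival. The AE incidence on placebo is also assumed and shown as a range, because the protocol gives none.

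**1. The plan's own figure.** Hazards per month are −ln(0.70)/18 = 0.01982 and −ln(0.85)/18 = 0.00903, so the hazard ratio is 0.456. The Lakatos log-rank method with 6 months of accrual and 18 months of follow-up gives 211.04, i.e. 106 per group or 212 in total. Then 212/0.85 = 249.4, i.e. 250, and 250/0.90 = 277.8, i.e. 278. The protocol's 106, 212, 250 and 278 all reproduce, so these hazards represent its planning scenario.

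**2. Observation time.** Mean time to month 18 is (1 − S)/λ.
- Control: 0.30/0.01982 = 15.14 months.
- Rasagiline: 0.15/0.00903 = 16.61 months.
- Ratio: 1.097.

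With 15% drop-out in each arm the means are 14.04 and 15.37 months (ratio 1.094). With follow-up to a common close at 18 to 24 months they are 17.16 and 19.12 months (ratio 1.114).

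**3. Crude incidence when the AE hazard is equal.** With a constant AE hazard r in both arms and death competing, the share of patients with an event by month 18 is r/(r + λ) × [1 − exp(−18(r + λ))].

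For 50% on placebo, r = 0.04815 per month:
- Control: 0.04815/0.06797 × [1 − exp(−1.2234)] = 0.7085 × 0.7058 = 50.0%.
- Rasagiline: 0.04815/0.05718 × [1 − exp(−1.0292)] = 0.8421 × 0.6427 = 54.1%.

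**4. Rejection rate of the two-sided 5% chi-square test, 125 per arm.** Let d be the difference and p̄ the mean of the two proportions. Let SE0 = √(2p̄(1 − p̄)/125) and SE1 = √((p1(1 − p1) + p2(1 − p2))/125). The rejection rate is Φ((d − 1.96·SE0)/SE1) + Φ((−d − 1.96·SE0)/SE1).

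For 50% on placebo, d = 0.0412, SE0 = 0.0632 and SE1 = 0.0631. This gives Φ(−1.31) + Φ(−2.61) = 0.095 + 0.004 = 10.0%, nearly all of it against rasagiline.

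| Placebo incidence (assumed) | Rasagiline, same hazard | Rejection at nominal 5% |
|---|---|---|
| 5% | 5.5% | 5.3% |
| 20% | 21.9% | 6.5% |
| 50% | 54.1% | 10.0% |
| 70% | 75.0% | 14.2% |
| 90% | 94.1% | 22.2% |

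**5. Where the effect fades.**
- Equal survival: the two percentages are identical and there is no distortion.
- Smaller benefit, assumed hazard ratio 0.75: mean observation on rasagiline is 15.79 months, and 15.79/15.14 = 1.043, about 4% more.
- Events confined to the first 3 months (the step 3 formula with 3 in place of 18): 50% on placebo becomes 50.7% and the test rejects 5.1% of the time. For 10% to 50% incidence the excess is 0.2 to 0.7 points.

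**6. Patient-year rates as the remedy.** For the early events just described, dividing by total observation time gives a rate ratio of (50.7/16.61)/(50/15.14) = 0.92, although the hazards are equal. A rate per 100 patient-years can therefore err in the other direction, in favour of the arm observed longer.

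**The case against.** The strongest reply is that the chi-square test is a valid test of a meaningful quantity: the share of patients who experience an event by 18 months, with death competing. It misleads only if one wants the event rate while patients are alive and observed, and the protocol does not say which it wants. Section 7 leaves detail to a statistical analysis plan, which could add person-time rates. The safety analyses are exploratory, and no multiplicity control is stated for them, so a rejection rate of 6% to 14% instead of 5% changes little. This stands and is why the point is minor. It does not remove the point, because a between-group comparison is named and its result will be read as a statement about safety.

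Three stronger readings are tempting and are not supported.
- A reader might infer that the method is biased against rasagiline whatever happens. The distortion needs a survival difference, and its size depends on the type of event.
- A reader might infer that, if the drug shortened survival, the method would hide harm. Non-fatal events would then be under-counted. Deaths, however, are serious adverse events (6.2.2.1) and the primary endpoint (3.3), and the data safety and monitoring board reviews safety data every three months, with unblinded data on request (10.8). For fatal events the direction also reverses: a survival benefit lowers their count on rasagiline.
- A reader might infer that patient-year rates should replace the chi-square test. Step 6 of the working shows that they carry a bias of their own for early events.

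**Conclusion.** The point holds as a minor, conditional one. Under the protocol's own 70% against 85%, rasagiline patients have about 10% more observation time (9.4% to 11.4% across the drop-out and follow-up assumptions). For common events that accrue throughout the 18 months, equal hazards then give a crude excess of about 2 points at 20% incidence, 4 at 50% and 5 at 70%. The nominal 5% test rejects in about 6.5%, 10% and 14% of trials respectively.

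These figures rest on exponential survival, a constant AE hazard that is equal in both arms, assumed placebo incidences, and full realisation of the planned effect. No confirmatory conclusion is affected.

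**What to change.** Keep the crude frequencies and the chi-square tests. In the synopsis and in 7.4, add for common AEs a comparison that accounts for time at risk, as one or both of:
- time to first AE, with a cause-specific hazard ratio and 95% confidence interval, censoring at death or last contact;
- incidence per 100 patient-years by arm, with rate ratio and 95% confidence interval, and a note that it assumes a constant hazard and can favour the longer-observed arm for early-onset events.

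Make the synopsis and 7.4 state the same between-group comparison.

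The cost is a little extra analysis and one more column per safety table. Sample size, visits and patient care are unchanged. The date of last contact is defined in 7.3.1. Section 7.4 lists the duration of each AE and the sample form in Appendix III has an onset date for serious events, so it only needs confirming that the case report form holds an onset date for every AE.

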## **Trial schedule**

Visit	Screening (V0)	Baseline (V1)	T1	V2	T2	V3	Т3	V4	T4	V5
Months		Inclusion	1	2	3	6	9	12	15	18
Patient information and informed consent	Х									
Inclusion/exclusion criteria checking	Х	Х								
Demographics (e.g. sex, age, race)	Х									
Medical history	Х									
Vital capacity	Х	Х		Х		Х		Х		Х
Status (El Escorial Criteria)	Х									
Randomization		Х								
Concomitant treatment	Х	Х	Х	Х	Х	Х	Х	Х	Х	Х
Physical examination	Х									
Vital signs	Х	Х		Х		Х		Х		Х
Height (only at screening), Weight	Х	Х	Х	Х	Х	Х	Х	Х	Х	Х
ALSFRS-R		Х	Х	Х	Х	Х	Х	Х	Х	Х
SEIQoL		Х		Х		Х		Х		Х
Study Drug delivery		Х		Х		Х		Х		
Drug Accountability				Х		Х		Х		Х
Laboratory tests	Х	Х		Х		Х		Х		Х
Genetic testing (with consent of patient)		Х								
Pregnancy test (serum HCG level)	Х									
Compliance (asked for)			Х	Х	Х	Х	Х	Х	Х	Х
Adverse events		Х	Х	Х	Х	Х	Х	Х	Х	Х
End of trial (final visit)										Х

# 1 INTRODUCTION

## 1.1 Scientific background

Amyotrophic lateral sclerosis (ALS) is a severe neurodegenerative disease characterized by progressive degeneration of the anterior horn cells of the spinal cord, their homologues in the brain stem and the upper motor neurons in the primary motor cortex. Clinically, the disease progresses from initial asymmetric weakness, wasting and atrophy to complete loss of spinal and bulbar motor functions. The upper motor neuron component is clinically mirrored by hyperactive tendon jerks, pseudobulbar emotional lability, and less frequently spasticity.

The ALS Research Committee of the World Federation of Neurology has established research diagnostic guidelines, the El Escorial criteria [1, 2] (http://www.wfnals.org). ALS is considered an orphan disease: its incidence is estimated with 1.5 –3 /100000/year and prevalence rates are 3-6/100000 [3]. Treatment of ALS remains unsatisfactory; riluzole, a benzothiazole derivative and glutamate release blocker, has been approved for use in ALS because of its modest effect on survival [4]. The drug is generally well tolerated by the patients although liver toxicity must be controlled (http://www.cochrane.org).

Based on a rare cause of the disease, mutations in the gene for the cytosolic form of the copper/zinc superoxide dismutase (Cu/Zn SOD), a transgenic animal model has been developed. This G93A model of fALS has led to the discovery of several experimental drugs; in particular, a dose-dependent effect of rasagiline on survival (alone and in combination with riluzole) has been demonstrated in a mouse carrying a low copy number of the human disease-causing gene [5].

Rasagiline [N-propargyl-(1R)-aminoindan] is a selective irreversible second-generation monoaminooxidase (MAO)-B inhibitor with symptomatic efficacy in Parkinson's disease (PD) with a favourable tolerability profile [6]. Preclinical studies have demonstrated that rasagiline has neuroprotective effects both in in vitro and in vivo models, suggested to be related to its propargyl moiety rather than MAO inhibition. Structure activity studies have established that N-propargylamine is essential for the neuronal cell survival activity of rasagiline since this moiety itself revealed similar protective effects and mechanisms of actions [5]

The mechanisms underlying disease-modifying effects of rasagiline have been investigated in detail in another neurodegenerative disease. Clinical studies using rasagiline showed the following: the TEMPO trial demonstrated that early Parkinson's Disease (PD) patients who received oncedaily rasagiline (2 mg/d) for 1 year had significantly less deterioration in clinical scores than those who received 6 months of placebo treatment followed by 6 months treatment with 2 mg/d rasagiline [7]. The ADAGIO study [6] which had been designed to investigate prospectively the potential of rasagiline to delay disease progression and was performed in a total of 1176 patients with early PD. It could be demonstrated that early treatment with rasagiline 1 mg/d provided benefits that could not be achieved with delayed introduction of the same drug. These results are consistent with the hypothesis that rasagiline has a "disease modifying" effect, and possible explanations for such an effect could involve neuroprotection and/or preservation or enhancement of supportive compensatory mechanisms.

## 1.2 Trial rationale

ALS is seen as a rare disease; however, the current incidence rates in the industrialized world of 2.5-3/100000 imply that more than each 500th living German citizen will die of ALS. Up to now only one substance, riluzole, is approved for the treatment of patients with ALS [8]. However, this drug has only a modest effect on survival of these patients since - depending on the stage of the disease - this effect prolongs survival about three to six months. This situation remains unsatisfactory for the ALS patients and the physicians treating such patients. Therefore much more

effort is needed to develop further appropriate therapies that will slow or stop this devastating disease.

Rasagiline has demonstrated a significant, dose-dependent therapeutic effect on both preclinical and clinical motor function and survival of G93A mice. The largest extension of life span of about 20% was observed with the combination of riluzole and rasagiline and was also dose-dependent [5].

Rasagiline is an anti-apoptotic compound and has demonstrated neuroprotective effects in a variety of primary neuronal preparations and neuron-like cell lines [9]. Clinical studies have also demonstrated possible neuroprotective properties of rasagiline in human Parkinson patients who showed a decelerated disease progression after treatment with 1mg/day rasagiline (ADAGIO trial) [6].

These positive clinical results and the effects of rasagiline in the ALS mouse model justify a clinical study in patients with ALS.

Positive results of this trial could lead to a further development of the treatment of ALS patients.

### **1.3** Treatments and rationale for dose selection

Experimental group: Patients are treated with 100 mg/day riluzole (standard therapy for ALS) and additionally with 1mg/day rasagiline. Rasagiline is approved for the treatment of Parkinson's disease by the FDA and the EMA with a dose of 1mg/day and there is no evidence that additional benefit will be obtained from the administration of higher doses. Furthermore, higher doses will likely result in a loss of selectivity of rasagiline towards MAO-B with an increase in the inhibition of MAO-A.

Control group: Patients are treated with riluzole (standard therapy for ALS) and additionally with placebo.

The need for a double-blind, placebo-controlled, prospective trial is justified since - if positive – an attempt will be made to introduce rasagiline into routine treatment of ALS which needs to be accepted by the regulatory authorities (EMA, FDA).

